**Table 1. Assessments**

	Screening	Day 0 - First Infusion (Ketamine or Saline) and Day 0+28- Second Infusion (Ketamine or Saline)					Day 1 and Day 1+28	Day 2 and Day 2+28	Day 3 and Day 3+28	Day 5 and Day 5+28	Day 7 and Day 7+28	Day 10 and Day 10+28	Day 14 and Day 14+28
		-1 hour	0 hour	1 hour	2 hour	3 hour							
INTERVENTION													
Infusion			X										
BAT													
Impromptu Speech*		X					X				X		

MEDICAL ASSESSMENT												
Vital Signs												
Vital Signs	X	X	X	X	X	X						
Physical Exam	X	X				X						
EKG	X	X				X						
Blood Tests	X											
Urine Tests	X	X										
CLINICAL RATINGS												
SCID	X											
LSAS	X	X			X	X	X	X	X	X	X	X
SDS	X	X			X	X	X	X	X	X	X	X
VAS**	X	X	X	X	X	X	X	X	X	X	X	X
ASI		X										
SSPS**		X				X				X		
PANAS**		X				X				X		
BAI**	X	X			X	X	X	X	X	X	X	X
HAM-D	X	X			X	X	X	X	X	X	X	X
STAI**	X	X			X	X				X		X
CGI	X	X			X	X				X		X
OE		X										
TE					X	X				X		
MMSE	X	X	X	X	X	X						
BPRS-PS	X	X	X	X	X	X						
CADSS	X	X	X	X	X	X						

\*All ratings and tests are assessed before the impromptu speech on the behavioral assessment test (BAT) days

\*\*These ratings are assessed both before and after the impromptu speech on the behavioral assessment test (BAT) days

Table 1 presents the overall design of this study in terms of interventions, clinical ratings, behavioral assessments and laboratory examinations. A baseline screening assessment to determine study eligibility, clinical ratings, and physical health will be conducted at least one week prior to study enrollment. On the first study day, the patients will receive an infusion of ketamine or placebo, and the second infusion will be performed on day 28. A battery of clinical and cognitive rating scales will be employed to determine the effects of ketamine administration on mood, anxiety, perceptual distortions, and cognitive function for the first 3 hours and first 14 days following the placebo and ketamine infusion period. Twenty-eight days will separate the first and second infusions.

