Health Center Investigational Drug Service phone number, and regular hours telephone numbers of their study physician and research support staff ([name] [contact]), should unpleasant effects occur after the subject has left the testing facility. All participants are contacted 1, 2, 3, 5, 7, 10, 14, 21, and 28 days after each infusion for safety reasons. In addition, participants will be contacted 1, 2, 3, 5, 7, 10, and 14 days after each infusion to administer symptom ratings. Participants will be instructed and encouraged to contact the treatment team between scheduled meetings should their distress worsen.

In order to enroll in the study, patients must not have a lifetime history of substance abuse or dependence, thereby reducing the risk of ketamine substance abuse/dependence by study participants.

**Blood drawing/intravenous placement:** The risks of blood draws and intravenous line placements are rare, and when these are done under sterile conditions by trained personnel the occurrence is even more remote.

**Psychiatric evaluation, rating scales, questionnaires, speech tasks, and attention bias tasks:** In order to minimize risks associated with the psychiatric ratings and ensure the accuracy of reporting, these measures will be administered by a trained research nurse and supervised by a study physician. During the impromptu speech, participants have the option to stop the speech at any time if they experience significant distress.

**Clinical deterioration:** If a participant shows significant worsening of symptoms, he or she will be evaluated for clinically appropriate pharmacological and non-pharmacological treatments by a clinic psychiatrist and followed until successful contact with a community provider is made. Patients will be informed that the decision to initiate a course of psychotropic medication will not affect their eligibility to participate in future studies, to receive treatment at the Connecticut Mental Health Center or Yale, or to receive treatment on a private basis from a referring clinician.

**11. Data and Safety Monitoring Plan:** Include an appropriate Data and Safety Monitoring Plan (DSMP) based on the investigator's risk assessment stated below. (Note: the HIC will make the final determination of the risk to subjects.) For more information, see the Instructions, page 24.

- a. What is the investigator's assessment of the overall risk level for subjects participating in this study? This is a moderate risk study.

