and severity of the adverse events and determine if modifications to the protocol or consent form are required.

- d. For multi-site studies for which the Yale PI serves as the lead investigator: N/A
  - i. How will adverse events and unanticipated problems involving risks to subjects or others be reported, reviewed and managed?
  - ii. What provisions are in place for management of interim results?
  - iii. What will the multi-site process be for protocol modifications?

**12. Statistical Considerations:** Describe the statistical analyses that support the study design.

We will use a paired t-test to compare average improvement over the first 3 days following infusion between ketamine and saline. Ketamine greatly reduces anxiety and depressive symptoms in MDD with an effect size of 1.4-1.5 in similarly designed saline controlled studies (Zarate, Singh et al. 2006). If ketamine proves to be as efficacious in SAD as it is in MDD, a sample size of 18 would allow a placebo to ketamine comparison study to have statistical power greater than 0.80 to detect a statistically significant change at the  $\alpha = 0.05$  level (Cohen 1988). However, it is quite possible that the benefits of ketamine will be smaller in SAD than depression. Therefore, even if the results of our primary analysis are not statistically significant, we would consider having 6 of 18 patients exhibiting a response to ketamine (but not placebo) during the first week following infusion as sufficient evidence towards conducting a more definitive trial. Treatment response is defined as at least a 30% reduction in VAS scores anytime in the first 3 days following infusion.

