Ketalar is chemically designated *d,l* – 2- (0-chlorophenyl)-2-(methylamino) cyclohexanone hydrochloride. It is formulated as a slightly acidic (pH 3.5-5.5) sterile solution for intravenous or intramuscular injection in concentrations containing the equivalent of either 10, 50, or 100 mg ketamine base per milliliter and contains not more than 0.1 mg/mL Phemerol® (benzethonium chloride) added as a preservative. The 10mg/mL solution has been made isotonic with sodium chloride. The medication will be obtained and stored at the CMHC research pharmacy, and will be picked up by investigators on the morning of infusion.

Check applicable Investigational Drug Service utilized:

YNHH IDS  
 CMHC Pharmacy  
 PET Center

Yale Cancer Center  
 West Haven VA  
 None

Other:

*Note: If the YNHH IDS (or comparable service at CMHC or WHVA) will not be utilized, explain in detail how the PI will oversee these aspects of drug accountability, storage, and preparation.*

**5. Use of Placebo:**  Not applicable to this research project

If use of a placebo is planned, provide a justification which addresses the following:

a. Describe the safety and efficacy of other available therapies. If there are no other available therapies, state this.

Since this is a crossover trial, all subjects will receive both ketamine and placebo during the course of the study. A placebo control is necessary because there is a significant improvement with time and to treatment expectancy that occurs in anxiety disorders. Using a crossover design allows all subjects to get the research medication being studied in the protocol, yet provide an appropriate comparison condition.

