**[name]; [name], and [name].**

**9. Process of Consent/Accent:** Describe the setting and conditions under which consent/assent will be obtained, including parental permission or surrogate permission and the steps taken to ensure subjects' independent decision-making.

Investigators will obtain consent during a screening visit at the Yale Child Study Center. During this visit, all aspects of the study will be discussed and the inclusion criteria will be explained.

**10. Evaluation of Subject(s) Capacity to Provide Informed Consent/Accent:** Indicate how the personnel obtaining consent will assess the potential subject's ability and capacity to consent to the research being proposed.

Patients with SAD are considered capable of consent. Individuals with limited capacity to consent will not be enrolled in the study. The principal investigators and co-investigators responsible for consenting potential subjects will use their clinical judgment to determine whether potential subjects have the capacity to consent. Patients must be able to understand the study protocol, appreciate and rationally manipulate the risks and benefits, and verbalize their consent.

**11. Documentation of Consent/Accent:** Specify the documents that will be used during the consent/assent process. Copies of all documents should be appended to the protocol, in the same format that they will be given to subjects.

The Compound Authorization and Consent form is included in this application

**12. Non-English Speaking Subjects:** Explain provisions in place to ensure comprehension for research involving non-English speaking subjects. Translated copies of all consent materials must be submitted for approval prior to use.

Non-English speaking subjects will not be enrolled in this pilot study because the number of subjects is small and translating the rating scales and employing trained personnel to administer the assessments would be too time-intensive for this sample size.

**13. Consent Waiver: In certain circumstances, the HIC may grant a waiver of signed consent, or a full waiver of consent, depending on the study.** If you will request either a waiver of consent, or a waiver of signed consent for this study, complete the appropriate section below.

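### The fallback go rule gives two different response windows and ignores placebo-only responders, so a tie with saline can still count as a go

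*Combined protocol and SAP*

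**What the plan says.** The primary analysis is a paired t-test of average improvement over the first 3 days after each infusion (Section V, 1 and 12). Section V, 12 adds a fallback because "it is quite possible that the benefits of ketamine will be smaller in SAD than depression". It applies "even if the results of our primary analysis are not statistically significant", and treats "6 of 18 patients exhibiting a response to ketamine (but not placebo) during the first week following infusion as sufficient evidence" towards a larger trial. The sentence that follows defines treatment response as "at least a 30% reduction in VAS scores anytime in the first 3 days following infusion".

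On timing, Section V, 10 says "participants will be contacted 1, 2, 3, 5, 7, 10, and 14 days after each infusion to administer symptom ratings". Table 1 (Section V, 3) also lists VAS ratings on the infusion day. For the VAS and some other scales its footnote adds: "These ratings are assessed both before and after the impromptu speech on the behavioral assessment test (BAT) days". Section V, 12 does not say which of these readings enter the response definition.

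The rule sets no condition on placebo-only responders. No placebo response rate, within-patient correlation or false-go rate is given for it.

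**The concern.** A go rule fixed in advance is useful only if two people applying it to the same data reach the same answer. Here they may not: days 5 and 7 lie inside one stated window and outside the other.

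The second problem is the comparison. In a crossover the evidence for a drug effect on a yes/no response lies in the two discordant groups: patients who respond to ketamine only and patients who respond to saline only. The rule uses the first and ignores the second. Placebo-only responders are foreseeable, since the placebo justification in Section VI.A.5 says that "there is a significant improvement with time and to treatment expectancy that occurs in anxiety disorders".

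The clause matters most after a non-significant primary test. At stake is a decision to start a larger trial on a result that shows no advantage over saline, or a dispute over whether the threshold was met.

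**Working it through.** **Plan's own figure.** The only operating characteristic stated is power above 0.80 for the t-test with 18 patients and an effect size of 1.4 to 1.5. Read as the mean paired difference over its SD, two-sided 0.05, power exceeds 0.999. Read as a between-patient effect size with zero within-patient correlation, it is 0.977 to 0.989. Both agree with the plan. Neither bears on the 6-of-18 rule.

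**Window.** Scheduled rating days 1, 2 and 3 fall in both windows; days 5 and 7 fall only in the one-week window. A first 30% reduction on day 5 or 7 is a response by the criterion and a non-response by the definition.

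**One discordant group.** Let K be the number of ketamine-only and S the number of placebo-only responders. The rule, read as at least 6, is K ≥ 6. Results of 6 vs 6 and 6 vs 8 both pass.

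**How often this matters with an inert drug.** Assumptions, none from the documents: common response rate p, no period effect, all 18 complete. With independent periods each discordant cell has probability q = p(1−p). With latent bivariate-normal correlation ρ, q = p − Φ₂(z, z; ρ), where z = Φ⁻¹(p). Then K is Binomial(18, q), and (K, S) is trinomial with cells q, q, 1−2q.

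| p | q (independent) | P(K ≥ 6) | P(K ≥ 6 and K > S) | P(K ≥ 6 and S ≥ K) |
|---|---|---|---|---|
| 0.1 | 0.09 | 0.4% | 0.4% | <0.1% |
| 0.2 | 0.16 | 5.5% | 5.5% | 0.1% |
| 0.3 | 0.21 | 16% | 15% | 0.7% |
| 0.4 | 0.24 | 25% | 23% | 2.1% |
| 0.5 | 0.25 | 28% | 25% | 2.9% |

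Over the same range of p, P(K ≥ 6) is at most 14%, 6.5% and 2% at ρ = 0.3, 0.5 and 0.7. The tie-or-worse go in the last column is at most 0.5% at ρ = 0.3 and 0.1% at ρ = 0.5. If saline were truly better (40% vs 50%, independent periods), the rule passes in 13% of trials, or 11% with K > S added.

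**Cost of adding K > S when ketamine works.** Independent periods; ketamine-only cell p_k(1−p_s), placebo-only cell p_s(1−p_k).

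| True response, ketamine vs saline | K ≥ 6 | K ≥ 6 and K > S |
|---|---|---|
| 50% vs 10% | 89.2% | 89.2% |
| 60% vs 20% | 93.2% | 93.2% |
| 60% vs 30% | 83.7% | 83.3% |
| 40% vs 20% | 54.0% | 53.8% |
| 50% vs 30% | 64.5% | 63.7% |

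The largest loss is 64.5 − 63.7 = 0.8 points.

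**Effect of the window on the false-go rate.** Suppose each reading has chance r of showing a 30% drop, with readings and periods independent. Then p = 1 − (1−r)^k for k readings, and q = p(1−p).

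- r = 10%: 3 readings (days 1 to 3) give p = 27.1% and false-go 13%; 5 readings (days 1, 2, 3, 5, 7) give p = 41.0% and 25%.
- r = 20%: 3 readings give 28%; 5 readings give 19%. The order reverses, because q falls once p passes 0.5.
- r = 10%, with three post-infusion readings on day 0 also counted: 6 readings give 28%; 8 readings give 27%. The contrast disappears.

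The direction is therefore not fixed. It depends on r and on which readings count.

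**The case against.** The strongest reply is that the defining sentence governs. It defines the term used in the sentence before it, and its 3 days match the primary outcome. That is the natural reading and the reason to settle on 3 days. It does not remove the conflict, because the one-week phrase then has no function and the text does not say that it yields.

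Next, each patient is their own control, and a 6 vs 6 result needs 12 of 18 patients discordant. This stands as to frequency: tie-or-worse goes are rare under the null. It does not stand as to logic, since the rule as written accepts them.

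Finally, this is a pilot, as Section VII, 12 says: "Non-English speaking subjects will not be enrolled in this pilot study because the number of subjects is small". The criterion is worded softly and makes no confirmatory claim. That stands and keeps the severity low.

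Three stronger readings are tempting, and the documents do not support them.

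- A reader might infer that an inert drug would pass about a quarter of the time. That needs a 40% to 50% response to saline and zero within-patient correlation. The documents give neither figure, and positive correlation lowers the rate.
- A reader might infer that the longer window inflates false goes. The calculation shows no fixed direction.
- A reader might treat the unstated false-go rate as an error in itself. For a non-confirmatory pilot rule it is missing detail. A stricter threshold would trade away sensitivity to the smaller benefits for which the clause was written.

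**Conclusion.** The point holds in two parts. The rule contradicts itself on the response window, which follows from the text alone. It also accepts a tie or a result favouring saline as sufficient evidence, because it ignores placebo-only responders. With an inert drug and independent periods, that second outcome occurs in at most 2.9% of trials for response rates of 10% to 50%, and in fewer with positive correlation.

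The overall false-go range of 0.4% to 28% is illustrative only. It rests on assumed response rates, independent periods, no period effect and 18 completers. It is also unconditional: the rate given a non-significant primary test cannot be derived from the documents. Requiring more ketamine-only than placebo-only responders lowers it only slightly (28% to 25% at most), so that condition repairs the logic of the rule and does not recalibrate its threshold.

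Severity is low. The paired t-test and its power statement are unaffected.

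**What to change.** Before unblinding, amend Section V, 12 as follows.

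- Replace the one-week window in the criterion with the first 3 days, so that it matches the response definition and the primary outcome.
- State which VAS anxiety readings count: whether infusion-day readings are included, and whether the before-speech or after-speech reading is used on speech days.
- Require at least 6 ketamine-only responders and more ketamine-only than placebo-only responders.
- Report both discordant counts whatever the result.

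The cost is a few sentences. No new data are needed, since both counts come from VAS records already planned. The chance of a correct go falls by at most 0.8 points in the five scenarios above. A patient whose first response comes on day 5 or 7 would no longer count, which is already so under the plan's own definition of response.

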**SECTION VI: RESEARCH INVOLVING DRUGS, BIOLOGICS, RADIOTRACERS, PLACEBOS AND DEVICES**

*If this section (or one of its parts, A or B) is not applicable, state N/A and delete the rest of the section.*

**A. DRUGS, BIOLOGICS and RADIOTRACERS**

1. **Identification of Drug, Biologic or Radiotracer:** What is (are) the **name(s)** of the drug(s) biologic(s) or radiotracer(s) being used? Identify whether FDA approval has been granted and for what indication(s).

Ketamine (Ketalar) has USDA approval as the sole anesthetic agent for diagnostic and surgical procedures that do not require skeletal muscle relaxation. The drug is also indicated for the induction of anesthesia prior to the administration of other general anesthetic agents or to supplement low potency agents, such as nitrous oxide. In this study, ketamine will be used for a therapeutic purpose. Nonetheless, [name] holds the research license for administering this controlled substance in a non-therapeutic research study.

All protocols which utilize a drug, biologic or radiotracer **not** approved by, but regulated by, the FDA, or a radiotracer regulated by the RDRC, must provide the following information: **N/A**.

- a. What is the Investigational New Drug (IND) **number** assigned by the FDA?

b. Who holds the IND?

c. All protocols which utilize a radiotracer not approved by, but regulated by the FDA must provide the IND number: \_\_\_\_\_

Alternatively, use of the investigational radiotracer may be under RDRC/RSC oversight: (check if appropriate) \_\_\_\_\_

For all investigational radiotracers, attach a copy of the RDRC/RSC application (for radioisotopes used in the PET Center, PET Center personnel may complete this step) Go to <http://rsc.med.yale.edu/login.asp?url=myApps.asp>. When you have logged in, complete the application and attach a copy to this submission.

Alternatively, an **exemption from IND filing requirements** may be sought for a clinical Investigation of a drug product that is lawfully marketed in the United States. If there is no IND and an exemption is being sought, review the following categories and complete the category that applies (*and delete the inapplicable categories*):

### **Exempt Category 1**

The clinical investigation of a drug product that is lawfully marketed in the United States can be exempt from IND regulations if all of the following are yes:

- i. The intention of the investigation is NOT to report to the FDA as a well-controlled study in support of a new indication for use or to be used to support any other significant change in the labeling for the drug.  Yes  No
- ii. The drug that is undergoing investigation is lawfully marketed as a prescription drug product, and the intention of the investigation is NOT to support a significant change in the advertising for the product.  Yes  No
- iii. The investigation does NOT involve a route of administration or dosage level or use in populations or other factor that significantly increases the risks (or decreases the acceptability of the risks) associated with the use of the drug product.  Yes  No
- iv. The investigation will be conducted in compliance with the requirements for institutional (HIC) review and with the requirements for informed consent of the FDA regulations (21 CFR Part 50 and 21 CFR Part 56).  Yes  No
- v. The investigation will be conducted in compliance with the requirements regarding promotion and charging for investigational drugs.  Yes  No

2. **Background Information:** Provide a description of previous human use, known risks, and data addressing dosage(s), interval(s), route(s) of administration, and any other factors that might influence risks. If this is the first time this drug is being administered to humans, include relevant data on animal models.

Ketamine is a medication approved by the Food and Drug Administration to be used as an anesthetic. It is a dissociative anesthetic that has been used in humans since the late 1960's (32). Despite extensive experience there is no clear evidence of long-term toxicity associated with ketamine administration (33). Please see Risks and Minimizing Risks Sections labeled "Ketamine Administration" above.

**3. Source:** a) Identify the source of the drug or biologic to be used.

Ketamine (Ketalar) will be obtained from the CMHC Research Pharmacy

b) Is the drug provided free of charge to subjects?  Yes  No  
If yes, by whom?

**4. Storage, Preparation and Use:** Describe the method of storage, preparation, stability information, and for parenteral products, method of sterilization and method of testing sterility and pyrogenicity.

Ketalar is chemically designated *d,l* – 2- (0-chlorophenyl)-2-(methylamino) cyclohexanone hydrochloride. It is formulated as a slightly acidic (pH 3.5-5.5) sterile solution for intravenous or intramuscular injection in concentrations containing the equivalent of either 10, 50, or 100 mg ketamine base per milliliter and contains not more than 0.1 mg/mL Phemerol® (benzethonium chloride) added as a preservative. The 10mg/mL solution has been made isotonic with sodium chloride. The medication will be obtained and stored at the CMHC research pharmacy, and will be picked up by investigators on the morning of infusion.

Check applicable Investigational Drug Service utilized:

YNHH IDS  
 CMHC Pharmacy  
 PET Center

Yale Cancer Center  
 West Haven VA  
 None

Other:

*Note: If the YNHH IDS (or comparable service at CMHC or WHVA) will not be utilized, explain in detail how the PI will oversee these aspects of drug accountability, storage, and preparation.*

**5. Use of Placebo:**  Not applicable to this research project

If use of a placebo is planned, provide a justification which addresses the following:

a. Describe the safety and efficacy of other available therapies. If there are no other available therapies, state this.

Since this is a crossover trial, all subjects will receive both ketamine and placebo during the course of the study. A placebo control is necessary because there is a significant improvement with time and to treatment expectancy that occurs in anxiety disorders. Using a crossover design allows all subjects to get the research medication being studied in the protocol, yet provide an appropriate comparison condition.

Before beginning the study, participants will be informed of typical first-line treatments for SAD. Generally, one would try all three first line treatments sequentially followed by an MAOI as standard of care treatment(Pilling, Mayo-Wilson et al. 2013). However, roughly one-third to one-half of patients with generalized SAD do not experience significant clinical benefit from the combination of first-line interventions such as pharmacotherapy with selective serotonin reuptake inhibitors (SSRI), venlafaxine, or cognitive behavioral therapy (CBT) (Blomhoff, Spetalen et al. 2001, Davidson 2004, Baldwin, Anderson et al. 2005). Benzodiazepines, gabapentin, pregabalin, and monoamine oxidase inhibitors phenelzine and moclobemide are also effective in the treatment of social anxiety; however, to our knowledge, there are no randomized, placebo-controlled studies that examine the treatment of SAD patients who do not respond to first-line treatments. Moreover, aside from benzodiazepines, which have significant abuse potential, the medications often take at least a week for the patient to experience

benefits. This delay in anxiolytic effect coupled with side effects, which often begin immediately, can lead to premature discontinuation of these treatments. Finally, there is little evidence that combination of interventions (pharmacologic or psychotherapeutic) is effective(Blanco, Bragdon et al. 2013) (Blomhoff, Spetalen et al. 2001, Baldwin, Anderson et al. 2005).

b. State the maximum total length of time a participant may receive placebo while on the study.

One dose of IV saline will be given, and the patient will not receive the ketamine infusion one month (psychotropic medication changes are not allowed for the duration of the study – two months).

c. Address the greatest potential harm that may come to a participant as a result of receiving placebo.

Anxiety symptoms may not improve or even worsen depending on the clinical course of illness. Subjects have the option of withdrawing from the research protocol at any point if their symptoms worsen. Additionally, inpatient hospitalization resources are available to the investigator if subject's symptoms worsen to the point of requiring inpatient hospitalization as part of the protocol.

d. Describe the procedures that are in place to safeguard participants receiving placebo.

As stated in the “Minimize Risk” section under “Clinical Deterioration above, if a participant shows significant worsening of symptoms, he or she will be evaluated for clinically appropriate pharmacological and non-pharmacological treatments by a clinic psychiatrist and followed until successful contact with a community provider is made. Patients will be informed that the decision to initiate a course of psychotropic medication will not affect their eligibility to participate in future studies, to receive treatment at the Connecticut Mental Health Center or Yale, or to receive treatment on a private basis from a referring clinician.

